Our pilot study which showed a significantly increased change in FRC at the end of the two week treatment period and at discharge in the infants randomized to the additional two weeks of CPAP versus CPAP discontinuation is very encouraging ¹⁶. However the measurements in the pilot study were limited to those done in the NICU and did not measure lung diffusion which currently cannot be measured in the NICU. This new randomized trial will allow us to measure the persistence of the effect of eCPAP on lung volumes and to measure the effect on lung diffusion at six months of age. It will also allow us to measure the effect of eCPAP on forced expiratory flows and other exploratory outcomes including clinical respiratory and neurodevelopmental outcomes.

4. Study Design

[figure not shown]
a. Overview

This is a randomized single-blind Phase 2 trial of eCPAP in 100 stable preterm infants born at 24 to \leq 32 weeks of gestational age (**Figure 9**, Study Overview). Once infants are consented and, meet CPAP stability criteria they will be randomized to one of two groups:

- 1. 2 additional weeks of CPAP (eCPAP)
- 2. CPAP discontinuation as per usual NICU care (dCPAP)

Prior to randomization and at the end of the 2 weeks of treatment, a pulmonary function test (PFT) will be performed. Infants will return to OHSU at approximately 6 months of corrected gestational age (CGA) for pulmonary function (primary outcome of alveolar volume). Neurodevelopmental testing will be done at 6-12 months of age. Infants will be followed up to 1 year of age with monthly respiratory questionnaires that will be completed via phone. The study will be performed at OHSU and at PeaceHealth SouthWest Washington Medical Center (PHSW) and build on [name] strong pilot data¹⁶. It is not feasible or ethical to blind the caregivers and researchers to the randomized intervention in the NICU; however, the 6 month PFTs will be directed by personnel blinded to treatment allocation in the NICU and blinded personnel will administer the monthly respiratory questionnaires and neurodevelopmental assessments. The individual PFTs will be reviewed for acceptability, reproducibility, and completeness by [name], (Co-PI of study) and [name], RRT, an experienced infant pulmonary function technologist. They will be blinded to the treatment allocation as will the statisticians analyzing the final data.

Figure 9. Study Overview

5. Study Population

a. Number of Subjects

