Infants will be recruited in the 44 bed NICU at OHSU where [name] is the Director of Neonatal Research and the 20 bed NICU at PHSW where the OHSU neonatology division also provides NICU services. The OHSU Neonatal Division has extensive experience with bubble CPAP which has been the standard therapy of preterm infants for > 15 years at OHSU. The Neonatal Division follows extensive clinical consensus guidelines (CCG) with regards to important aspects of patient care including: enteral feeds, transfusions, septic workups among others. This will provide critical consistency to the proposed eCPAP study for the multiple aspects of patient care. Most importantly, the CPAP CCG since 2014 establishes bubble CPAP via Hudson prongs as the only CPAP delivery system used in the OHSU NICU and outlines the following practice as usual care at OHSU: when an infant meets CPAP stability criteria for at least 12 hours, the CPAP is discontinued and the infant is placed on room air. This CCG was established after review of limited published evidence to provide consistent weaning of preterm infants on CPAP. In NICUs worldwide, there are many different approaches to weaning patients off CPAP^{87;88} even within the same NICU. The consistent approach at OHSU and PHSW is an exception and will minimize potential confounders to our results.

f. Recruitment Methods

Recruitment will be maximized by having a specific NICU research coordinator screen daily for subjects, maintain a screening log, and consent subjects. Daily review of eligibility and CPAP stability criteria for individual patients will be performed with the neonatologist and bedside nurse. The study will be introduced to parents whose infant meets the screening criteria (24 to ≤ 32 weeks gestation and on CPAP). The infant will be

consented after inclusion and exclusion criteria are verified and randomized when CPAP stability criteria are met for at least 12 hours.

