The informed consent process will be an ongoing active process of sharing information between the investigator and the parent/legal guardian(s). If a protocol change requires a change to the consent form, parents/legal guardian(s) will be notified in a timely manner and the new informed consent form will be signed. Parent(s)/guardian(s) can withdraw from the study at any time. The study PI can discontinue a subject from the study at any time for safety concerns. Assent will not be obtained as the subjects in this study are neonates.

Permission may be obtained from legally authorized representatives, described as an individual who is authorized under applicable state or local law to consent on behalf of a child to general medical care when general medical care includes participation in research. Non-English speaking subjects may be enrolled. We will utilize a translated consent in Spanish and the IRB approved short forms for other languages. We will obtain an "Investigator's Certification for Activities Preparatory to Research" from the OHSU IRB to examine records of infants preparatory to research that contain protected health information. The medical records will be reviewed to assess eligibility for this trial prior to approaching the parents to discuss consent.

h. Randomization Method and Blinding

Subjects will be randomized after meeting inclusion/exclusion criteria, being consented, and meeting the additional randomization criteria:

1) CPAP stability criteria met for at least 12 hours

The following CPAP stability criteria 16;86 has to be met for more than 12 hours:

- o CPAP of 5 cmH2O
- o On room air
- Respiratory rate ≤70 bpm without significant retractions

- <3 self-resolving apneas or bradycardias or desaturations in 1 hour in last 6 hours
- Average SpO2 >86% for 90% of the last 24 hours
- o Not being treated for a patent ductous or sepsis
- o Tolerating CPAP "cares"

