Randomization will be done via REDCap by the data management team within strata defined by gestational age at delivery (28 and 6/7 and 29 and 0/7 weeks). If twins are both enrolled they will be allocated to the same treatment arm⁸⁹. A computer generated randomization scheme with stratum using random block sizes of 2 or 4 will be uploaded into REDCap for retrieval. The NICU team will know the treatment allocation but the follow-up research team assessing outcomes will be blinded to the treatment allocation. The electronic medical record will note the infant was in the study, but will not state allocation arm.

i. Assessment of Treatment Adherence

After randomization, the infant will be assessed daily by research staff for the 14 days on the assigned trial arm. As done in the pilot eCPAP study¹⁶, failure criteria for the respective randomization arms will be as follows: Infants randomized to dCPAP (usual care) will be defined as failing if they demonstrate:

- significantly increased work of breathing with a persistent respiratory rate > 75 breaths/ minute,
- o increased apnea and/or bradycardia and/or desaturations > 2 significant episodes in 1 hour in the past 6 hours,
- o oxygen need to maintain oxygen saturations > 86%,
- o a blood gas pH of < 7.2, PaCO2 > 65 mm Hg, or
- o major apnea or bradycardia needing resuscitation 16;86

Subjects who meet the criteria for failing dCPAP will be resumed on their previous level of CPAP. Another attempt to discontinue the subject's CPAP will occur within the next 5 days when they again meet the predefined stability criteria. If the subject does not meet the stability criteria or fails a second attempt at discontinuation, further weaning/management will be by the clinical team. The infant will continue to be studied as intention to treat. In our pilot study¹⁶, only 1 out of 26 subjects failed CPAP discontinuation.

Infants randomized to the eCPAP arm will have the CPAP stopped during the treatment period if there is significant abdominal distension with feeding intolerance or significant nasal breakdown (checked and documented every 3-4 hours as outlined in the OHSU NICU's CCG). The CPAP will be discontinued for up to 5 days and if symptoms resolve, the CPAP will be reapplied. If symptoms reoccur, the CPAP will be removed and further management will be by the clinical team. The infant will continued to be studied as intention to treat. In the pilot CPAP study¹⁶, all 22 patients tolerated eCPAP without adverse events.

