No studies have compared V_A at 6 month of age in stable preterm infants randomized to eCPAP versus dCPAP in the NICU. Data from our pilot eCPAP study showed a 12% higher FRC in stable preterm infants randomized to eCPAP versus dCPAP at the end of the two week treatment period¹⁶. A study by [name] et al reported a 16% difference in both V_A and D_L in preterm infants according to CPAP treatment in the NICU (Table 1)¹⁵ and a 12% difference in D_L between infants with BPD versus healthy term infants⁶⁹. Therefore, we powered our randomized trial to detect a 12% difference in V_A between the eCPAP and dCPAP groups.

Using an ANCOVA model and assuming a mean V_A of 642 mL (SD=189) based on data of the overall mean and SD from the control and CPAP groups reported in Assaf et al¹⁵, a sample size of 34 infants per group is needed to yield 80% power for detecting a 12% difference (effect size=0.42) in V_A in the eCPAP group at α =0.05 (Table 3). This sample size also allows us to detect a 12% difference in D_L with an effect size of 0.42. We estimate that 18% of the study samples will be twin pairs based on our pilot eCPAP study. Conservatively counting just one infant out of each twin pair for the sample size estimation, we will need 38 infants per group (76 total infants at 6 months) with completed V_A outcomes. We further conservatively project a 10% loss in the NICU and a 15% loss from NICU discharge to the 6 month PFT (due to preterm population and need to be at least 3 weeks after a respiratory infection for the performance of the PFT) and therefore we project we will

Table 3. Estimated power for 34 infants per group with completed PFT data

[figure not shown]
		Mean (SD) in	Estimated Power for Group Difference		
Outcome Measures		Control Group	12%	15%	17%
Alveolar volume (V _A)	Primary Outcome	642 (189)	80	92	97
Lung diffusing capacity (D _L)	Secondary Outcome	4.1 (1.19)	80	92	98

need to randomize 50 infants per group (total n=100) into the trial. This sample size will provide 80% power for detecting an effect size difference of 0.42 in outcome measures between the two groups in Aim 1 (primary outcome of V_A) and Aim 2 for D_L . This sample size allows us to detect a 23% difference in FEF₅₀. Figure 12 shows the projected study recruitment to achieve the desired sample size based on recruitment and cohort

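### Small blocks (2 or 4), disclosed in the protocol, leave next allocations partly guessable by NICU staff who also take part in deciding when an infant is ready to be randomized

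*Protocol*

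**What the plan says.** - **Sequence.** Protocol 5.h: "A computer generated randomization scheme with stratum using random block sizes of 2 or 4 will be uploaded into REDCap for retrieval". Lists are kept "within strata defined by gestational age at delivery (28 and 6/7 and 29 and 0/7 weeks"), which gives two strata. Site is not named as a stratum, so the two NICUs appear to share each list. The data management team performs the randomization in REDCap.
- **Knowledge of past allocations.** Protocol 5.h: "The NICU team will know the treatment allocation but the follow-up research team assessing outcomes will be blinded to the treatment allocation". Protocol 4.a (Overview): "It is not feasible or ethical to blind the caregivers and researchers to the randomized intervention in the NICU".
- **Trigger for randomization.** Protocol 5.f: "Daily review of eligibility and CPAP stability criteria for individual patients will be performed with the neonatologist and bedside nurse". A consented infant is randomized once the criteria have held for at least 12 hours. Most criteria are numeric, but part of one is a judgement ("Respiratory rate ≤70 bpm without significant retractions"), and so is tolerance of CPAP cares.
- **Numbers.** Section 5.a allows up to 130 consented infants for 100 randomized. Section 7.a gives 50 per group.
- **Not addressed.** Neither document discusses predictability, withholds the block sizes from site staff, or plans a check for selection at entry.

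**The concern.** A concealed list stops staff from reading the next assignment. It does not stop them from inferring it from assignments already made. With small balanced blocks in an open-label setting, the arm that is behind in the stratum is more likely to come next. If those who help judge readiness hold a view on which infants suit which arm, they can influence which of two ready infants is entered first, whether a borderline infant is called stable today, or whether an infant is entered at all. The groups would then differ at entry for reasons other than chance. Blinding the 6-month lung function testers and the statisticians protects measurement and analysis, but does not repair such a difference.

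**Working it through.** The plan gives no predictability figure, so there is none to reproduce.

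**Inputs.** Block sizes 2 and 4, two gestational-age strata and 1:1 allocation come from Protocol 5.h and 7.a. Assumptions: the sizes are equally likely (the mix is not stated), each stratum has 50 list entries, and a second twin, who takes the first twin's arm, uses no entry.

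**Strategy.** Guess the arm that is behind in the stratum, and toss a coin when the arms are tied.

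**Exact count, full stratum history known**

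A block of 4 has three patterns up to swapping the arms: AABB, ABAB and ABBA. Expected counts per block are:

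| | Block of 2 | Block of 4 |
|---|---|---|
| Correct guesses | 0.5 + 1 = 1.5 | (2.5 + 3 + 3)/3 = 2.833 |
| Allocations with arms not tied | 1 | (3 + 2 + 2)/3 = 2.333 |
| Of these, guessed correctly | 1 | 2 |
| Known with certainty | 0 | 2/3 (only after AA or BB) |

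The mean block length is (2 + 4)/2 = 3, so two blocks, one of each size, hold 6 allocations on average.

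- Correct guesses: (1.5 + 2.833)/6 = 72.2%.
- Informed guess available: (1 + 2.333)/6 = 55.6%.
- Informed and correct: (1 + 2)/6 = 50.0%, so informed guesses are right 50.0/55.6 = 90% of the time.
- Certain: (2/3)/6 = 11.1%.

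After the first allocation of a new block, the other arm follows with probability 0.5 × 1 + 0.5 × 2/3 = 5/6.

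**Range over the unknown mix.** The correct-guess rate runs from 70.8% (all blocks of 4) to 75.0% (all blocks of 2).

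**Simulated Bayesian observer, 4,000 lists of 50, equal mix of sizes**

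| Blocks | Correct | Probability at least 75% | Certain |
|---|---|---|---|
| 2/4 | 72% | 55% | 11% |
| 4/6/8 | 68% | 35% | about 2% |

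The 2/4 row agrees with the exact count.

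**One site's history only.** Protocol 10.f (Table 4) gives OHSU admissions of 113, 118, 128, 94 and 120, a mean of 114.6 a year, against about 50 a year at PHSW. Taking admissions as a proxy for randomizations, the OHSU share is 114.6/164.6 = 70%. With the other site's allocations hidden, the same observer is right for about 63% of allocations at OHSU (0.635) and 57% at PHSW, and no allocation is certain at either site.

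**The case against.** The opposing case has weight.

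- **Incomplete history.** The 72% needs a record of every allocation by stratum at both NICUs, and no section gives bedside staff such a record. This stands, and is why the one-site figures matter. On the other side, research staff assess each randomized infant daily for 14 days (5.i), a research coordinator screens daily and keeps the log (5.f), and one neonatology division serves both units (5.e). Fuller knowledge is therefore plausible, though not documented.
- **Limited room to steer.** Delaying an infant changes its likely arm only if another infant in the same stratum is randomized meanwhile. At 3 infants a month (10.d) over two strata, assumed equal, that is 1.5 per stratum per month, or about one every 20 days. Usual care stops CPAP once stability has held for 12 hours (5.e), so holding an infant back would be visible. This stands for long delays. It does not cover choosing between two infants ready together, a borderline call, or not entering an infant.
- **Mostly objective trigger.** This is largely correct. Clinical instability is an exclusion criterion checked before consent, not part of the trigger, and should not be counted as discretion at randomization.
- **Existing safeguards.** Baseline comparisons are planned, and variables that differ significantly enter the model (Protocol 7.b1; SAP, Specific Aim 1). A modest shift could miss significance, and baseline FRC is not a named covariate for V_A.

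A reader might infer that printing the block sizes is the main fault. It is not: guessing the lagging arm gives the same 72% without knowing them. Disclosure mainly tells staff which allocations are certain.

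**Conclusion.** The weakness is real but moderate. With full stratum history at both sites and an equal mix of block sizes, about 72% of next allocations can be guessed, about 55% on an informed basis and about 11% with certainty. One site's history gives about 63% or 57%.

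Two stronger readings are tempting, and the documents support neither.

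- **Staff can predict most allocations.** The 72% includes coin tosses at ties. Informed and correct guesses make up half of allocations, and only for someone holding the whole history.
- **The bias can be stated in millilitres.** If infants entered under opposite guesses differed by 0.25 SD, the formula (2 × 0.722 − 1) × 0.25 × 189 gives 21 mL, or 27% of the 77 mL target (0.12 × 642). But the 0.25 SD has no source in the documents. The formula also treats every entry as steered by a full-history observer, and uses the raw SD although the model adjusts for length and sex. It is not an expected bias.

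Nothing in the documents shows that entry was or would be steered. What is established is an avoidable opening with no planned check. The change is worth making because it is cheap.

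**What to change.** **If randomizations remain.** Drop blocks of 2 and use larger varying blocks, such as 4, 6 and 8. Keep the block details in a file restricted to the data management team, and take them out of the protocol. Certain allocations fall from 11% to about 2%, and those with at least 75% probability from 55% to 35%. Correct guesses fall only from 72% to 68%, so the gain lies mainly in removing near-certain predictions. A big-stick rule with a maximum imbalance of 3 lowers correct guesses further, to 58%, but 16% of allocations are then forced, more than the 11% now certain, so it is not clearly preferable.

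**If the list is used up.** The SAP is dated August 2023, and the documents do not say how many randomizations remained. In that case add a sensitivity analysis to the SAP. For each list entry, compute the probability of eCPAP given the earlier allocations in that stratum. Regress pre-randomization FRC, already collected under Protocol 6.c, on that probability; without selection at entry there should be no association. Then repeat the V_A comparison with the probability as an added covariate. The primary analysis is unchanged.

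**Cost.** A new list upload with slightly larger possible within-stratum imbalance (up to 4 rather than 2), or one extra analysis.
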